6.2.2.2. Definitions of Assessment Windows for Adverse Events

To allow comparison between safety in active treatment vs placebo, and loading dose vs no loading dose, selected safety displays will be presented by study Weeks 1-12, Weeks 13-24, and Weeks 25-48. Adverse events are not associated with a specific visit therefore the study week they are assigned to will be based on the AE start date.

Analysis	Parameter	Analysis Window		Analysis	
Set / Domain	(if applicable)	Beginning Timepoint	Ending Timepoint	Timepoint	
Adverse	All				
Events		1	81	Weeks 1 – 12	
		82	165	Weeks 13 – 24	
		166	-	Weeks 25 – 48	

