Soluble Protein (immunology)	Χ					Χ				Х
PAXGene RNA for expression analysis in whole blood	Χ				Χ					
OPTIONAL: Genetics	Χ									
Archived Samples [serum; plasma]	Χ				Χ		Χ		X	

- 1. In selected countries/sites, participants will have the option to use a centralised home nursing provider. Only selected visits will have the option to be performed as a home visit, these will include drug administration, blood draws, participant assessments and data collection. The full specifications of the home nursing services will be outlined in the SRM
- 2. A WOCBP must have both:
 - a. A confirmed menstrual period prior to the first dose of study intervention; additional evaluation (e.g., amenorrhea in athletes, birth control) should also be considered
 - b. AND a negative highly sensitive pregnancy test [urine or serum] within 24 hours before the first dose of study treatment
- 3. Hematology- platelet count to be analyzed at local laboratory prior to dose; hematology samples to be collected for central laboratory assessments in parallel
- 4. Only for selected sites able to transport to the analysis lab as specified in the SRM.

Table 3 On-Treatment: Day 57 to Day 162

Assessments ¹	D57	D64	D71	D78	D85	D92	D99	D106	D113	D120	D127	D134	D141	D148	D155	D162
Window		u.				I.	I.	± 3 c	days		I.	I.				-
	W9	W10	W11	W12	W13	W14	W15	W16	W17	W18	W19	W20	W21	W22	W23	W24
Study treatment dosing	Х	Х	Χ	Х	Χ	Х	Χ	Χ	Х	Х	Χ	Χ	Х	Χ	Χ	Χ
Safety Assessments																
AE/SAE review	Χ	Χ	Χ	Х	Χ	Χ	Χ	Χ	Χ	Х	Χ	Χ	Χ	Χ	Χ	Х
Concomitant medication review	Χ	Χ	Χ	Χ	Χ	Χ	Χ	Χ	Χ	Χ	Χ	Χ	Χ	Χ	Χ	Χ
Symptom directed exam	Χ				Χ				Χ				Χ			
Vital signs	Х	Χ	Χ	Χ	Х	Χ	Χ	Χ	Х	Х	Χ	Χ	Х	Х	Χ	Х
Injection site reactions	Χ	Χ	Χ	Χ	Χ	Χ	Χ	Χ	Χ	Х	Χ	Χ	Χ	Χ	Χ	Χ
Questionnaire (cell phone app, optional)																Х
Questionnaire (patient feedback on dosing regimen)																Х
Laboratory																
Pregnancy test (women of child bearing potential)	Х				Х				Х				Х			
Hematology ² [includes platelet count and WBC]	Х	Х	Х	Х	Х	Х	Х	Χ	Х	Х	Х	Х	Х	Х	Χ	Х
PT, INR, aPTT	Х				Х				Х				Х			
Chemistry	Х	Х	Χ	Х	Х	Х	Х	Х	Х	Х	Х	Х	Х	Х	Χ	Х
Urinalysis	Χ	Χ	Χ	Χ	Χ	Χ	Χ	Χ	Χ	Χ	Χ	Χ	Χ	Χ	Χ	Χ
Urine ACR	Χ		Χ		Χ		Χ		Χ		Χ		Χ		Χ	
HBsAg and HBV DNA	Χ	Χ	Χ	Χ	Χ	Χ	Χ	Χ	Χ	Χ	Χ	Χ	Χ	Χ	Χ	Χ
Anti- HBsAg	Χ				X				Χ				Χ			
Anti- HBeAg	Χ				Χ				Χ				Χ			
HBeAg (only for participants HBeAg positive at screening)	Х	Х	Χ	Х	Х	Х	Х	Χ	Х	Х	Х	Х	Х	Х	Χ	Х
HBV RNA, HBcrAg, and Sequencing (HBV Genotype/phenotype; HBV DNA and/or RNA)				Х				Х				Х				Х

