Pregnancy test (women of child bearing potential)	Х		Х	X	X	Х	Х	Х	Х
Hematology ² [includes platelet count and WBC]	Х	Х	Х	Х	Х	Х	Х	Х	Х
PT, INR, aPTT	Х		Х		Х	Х	Х	Х	Х
Chemistry	Х	Х	Х	Х	Х	Х	Х	Х	Х
Urinalysis	Х	Х	Х	Х	Х	Х	Х	Х	Х
Urine ACR	Х	Х	Х	Х	Х	Х	Х	Х	Х
HBsAg and HBV DNA	Х	Х	Х	Х	Х	Х	Х	Х	Х
Anti- HBsAg	Х	Х	Х	Х	Х	Х	Х	Х	Х
Anti- HBeAg	Х	Х	Х	Х	Х	Х	Х	Х	Х
HBeAg (only for participants HBeAg positive at screening)	Х	Х	Х	Х	Х	Х	Х	Х	Х
HBV RNA, HBcrAg, and Sequencing (HBV Genotype/phenotype; HBV DNA and/or RNA)	Х		Х		X		Х	Х	Х
Complement C3, Complement C4, hs-CRP, MCP-1		Х	Х	Х	Х	Х	Х	Х	Х

Assessments ¹	OT-Day 1	OT-Day 8	OT-Day 22	OT-Day 50	OT-Day 78	OT-Day 106	OT-Day 134	OT-Day 162	Early Termination
Window	±3 E	ays			±10	Days			
	OT- W1	OT-W2	OT-W4	OT-W8	OT-W12	OT-W16	OT-W20	OT-W24	
Complement C5a, Complement factor Bb		Х	Х	Х	Х	Х	Х	Х	Х
ANCA, Ang II	Х		Х	Х	Х	Х	Х	Х	Х
PK	Х	Х	X	X	X	Х	Х	Х	Х
PBMC Collection for immunophenotyping ³	Х				Х			Х	Х
Soluble Protein (immunology)	Х		Х		Х		Х	Х	Х
PAXGene RNA for expression analysis in whole blood	Х				Х			Х	Х
APRI/Fibrosure								Х	Х
Archived Samples [serum; plasma]	Х	Х	Х	Х	Х	Х	Х	Х	Х

- 1. In selected countries/sites, participants will have the option to use a centralised home nursing provider. Only selected visits will have the option to be performed as a home visit, these will include drug administration, blood draws, participant assessments and data collection. The full specifications of the home nursing services will be outlined in the SRM.
- 2. Hematology- platelet count analyzed at local laboratory is **optional** during the off-treatment period; hematology samples to be collected for central laboratory assessments (required; if local lab is being drawn, in parallel with local lab sample).
- 3. Only for selected sites able to transport to the analysis lab as specified in the SRM.

OT: off-treatment; the first off-treatment visit occurs 7 days after the last study treatment dose received, whether planned or last dose given after participant is withdrawn from study treatment (e.g., the planned first off-treatment visit occurs on Day 169, 7 days after the Day 162 visit; if participant is withdrawn from study treatment on Day 50, the first off-treatment visit occurs on Day 57)

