4. STUDY DESIGN

4.1. Overall Design

This is a Phase 2b, multi-center, randomized, partial-blind [Sponsor and Participant blinded], study to assess efficacy and safety of treatment with GSK3228836 in two populations of patients with CHB (1) participants on stable nucleos(t)ide treatment and (2) participants not currently on nucleos(t)ide therapy.

Both populations of patients with CHB will be randomized into one of 4 parallel arms:

- 300 mg GSK3228836 once/week for 24 weeks (plus loading dose of 300 mg GSK3228836 on Day 4 and Day 11);
- 300 mg GSK3228836 once/week for 12 weeks (plus loading dose of 300 mg GSK3228836 on Day 4 and Day 11) followed by step-down in dose of 150 mg (plus placebo to match to maintain participant blinding) GSK3228836 once/week for 12 weeks;
- 300 mg GSK3228836 once/week for 12 weeks (plus loading dose of 300 mg GSK3228836 on Day 4 and Day 11) followed by placebo once/week for 12 weeks;
- Placebo once/week for 12 weeks followed by 300 mg GSK3228836 once/week for 12 weeks (plus placebo loading doses to match on Day 4 and Day 11, no loading dose for GSK3228836 treatment)

After the 24 weeks of dosing with GSK3228836 or placebo, there will be a post-treatment follow-up period of 24 weeks.

Populations will be stratified based on HBsAg level (HBsAg \leq 3 log IU/mL and \geq 3 log IU/mL) and whether participants are HBeAg positive or negative.

The study is a partially blinded study where participants will be blinded to the study treatment. The investigators, site staffs and pharmacist will be unblinded. GSK and contract research organization (CRO) team members will be blinded to participants' study treatment and any potentially unblinding information, unless specified otherwise in the study blinding management plan (e.g., unblinded site monitors).

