6.2.3. Study Period

Assessments and events will be classified according to the time of occurrence relative to the study intervention period. Off Treatment Day 1 occurs 7 days after the last study treatment dose received, regardless of whether the participant completes treatment as planned or the participant is withdrawn from study treatment.

Study Intervention Period	Definition
Pre-Treatment	Date ≤ Study Treatment Start Date
On-Treatment	Study Treatment Start Date < Date ≤ Off Treatment Day 1 – 1 day
Post-Treatment	Date ≥ Off Treatment Day 1

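### The adverse-event period cuts at Days 82 and 166 fall three days before the planned Week 13 dose (Day 85) and the planned off-treatment start (Day 169), so a few Arm 4 placebo days are tabulated as active-period days

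*SAP*

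**What the plan says.** SAP 6.2.2.2 sets out a three-period split of adverse events, introduced with the words "To allow comparison between safety in active treatment vs placebo, and loading dose vs" no loading dose. It notes that adverse events do not belong to a visit, so "the study week they are assigned to will be based on the AE start date". The table ends the first period at Day 81 and continues with the rows "82 165 Weeks 13 – 24" and "166 - Weeks 25 – 48". SAP 4.5 gives the same purpose, limits the split to selected safety displays, and leaves the list of those displays to the programming specification. SAP 4.5.2 item 13 is one named example.

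The comparison rests mainly on Arm 4, which protocol 4.1 describes as "Placebo once/week for 12 weeks followed by 300 mg GSK3228836 once/week for 12 weeks". In the protocol's Schedule of Activities (Table 3) the dosing days run "D57 D64 D71 D78 D85 D92", so Week 12 is Day 78 and Week 13 is Day 85, each within ±3 days. The footnote to Table 4 of that schedule says that "the planned first off-treatment visit occurs on Day 169, 7 days after the Day 162 visit". SAP 6.2.3 agrees: "Off Treatment Day 1 occurs 7 days after the last study treatment dose received", and dates up to the day before count as on-treatment.

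**The concern.** A column meant to isolate active treatment should begin when active treatment begins. Day 82 does not correspond to any planned dose. It is the lower edge of the ±3-day window around the Week 13 visit, just as Day 166 is the lower edge of the window around the first off-treatment visit. Those windows appear in SAP 6.2.2.1, where a note restricts them to Early Termination visits. They exist to absorb variation in when a scheduled visit takes place. An adverse event is placed by its own start date, so a visit tolerance has no obvious role.

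What is at stake is the only concurrent placebo column for safety. If events that began before any active injection are shown in Arm 4's active period, the placebo column is slightly understated and the active column slightly overstated, in one direction. At the second cut, the last on-treatment days of every completing participant are shown with follow-up.

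**Working it through.** **Inputs**
- Period cuts: Days 1–81, 82–165, 166 onward (SAP 6.2.2.2).
- Nominal day of Week x: 1 + 7(x − 1) (SAP 6.2.2.1; agrees with the protocol schedule).
- Visit window for Day 57 to Day 162: ±3 days (protocol Table 3).
- Planned off-treatment start: Day 169 (protocol Table 4 footnote; SAP 6.2.3).
- Study Day 1: study treatment start date, which in Arm 4 is the first placebo dose (SAP 6.2.4).
- Arm 4 size: about 22 per population (SAP 5).

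**Step 1. Reproduce the plan's cuts**
- Week 12: 1 + 7 × 11 = Day 78. Week 13: 1 + 7 × 12 = Day 85. Week 24: 1 + 7 × 23 = Day 162.
- Off-treatment start: 162 + 7 = Day 169.
- Lower window edges: 85 − 3 = 82 and 169 − 3 = 166. These are the SAP's two cuts.

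**Step 2. First cut, Arm 4**

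With the Week 13 dose on Day d, the placebo period is Days 1 to d − 1. Placebo days tabulated in Weeks 13–24 number d − 82, for d from 82 to 88.

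| Week 13 dose day | Placebo days | Shown in Weeks 13–24 | Share |
|---|---|---|---|
| 82 | 81 | 0 | 0.0% |
| 83 | 82 | 1 | 1.2% |
| 84 | 83 | 2 | 2.4% |
| 85 (planned) | 84 | 3 | 3.6% |
| 86 | 85 | 4 | 4.7% |
| 87 | 86 | 5 | 5.8% |
| 88 | 87 | 6 | 6.9% |

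On schedule this is 22 × 3 = 66 person-days per population. No in-window dose day puts active time into Weeks 1–12, so the error runs only from placebo to active.

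**Step 3. Second cut**

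With the last dose on Day L, SAP 6.2.3 counts days up to L + 6 as on-treatment. The number of those days that fall in Weeks 25–48 is (L + 6) − 165 = L − 159. For L from 159 to 165 this gives 0 to 6 days, and 3 days (Days 166–168) at the planned L = 162. Arm 4 is on active drug by then, so no placebo event is involved.

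**Step 4. Period lengths**

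As written, Weeks 1–12 is 81 days and Weeks 13–24 is 165 − 82 + 1 = 84 days. Cuts at the planned dosing days would give Days 1–84 and 85–168, which is 84 days each.

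**Step 5. Would a fixed Day 85 cut be enough?**

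Only at nominal timing. A dose on Day 82 would leave 3 active days (82–84) in the placebo column; a dose on Day 88 would leave 3 placebo days (85–87) in the active column. A cut at the actual Week 13 dose date leaves none in either direction.

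**The case against.** The best defence is that the cuts may be deliberate. Day 82 is the earliest day on which the Week 13 dose may be given in window, and Day 165 (162 + 3) is the latest for the Week 24 dose. With in-window dosing, no active-drug day then enters Arm 4's placebo column and no dosing day enters Weeks 25–48. That trade-off is real, but the SAP does not state it, and cutting at the actual dose date gives the same protection without misplacing placebo days.

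A second point is that the periods are labelled by study week, not by treatment status, so they need not match SAP 6.2.3. This partly stands: the two schemes can coexist. But the cuts are also three days early against their own week labels on the planned schedule. A third point is that some start dates will be partial and imputed under SAP 6.2.6, with an error that can exceed three days. That is true for those events and is no reason to misplace fully dated ones.

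Several stronger readings are tempting, and the documents do not support them:
- **That both cuts turn placebo events into active ones.** Only the Day 82 cut can.
- **That events are thereby attributed to the drug.** Relationship to treatment is the investigator's assessment (SAP 4.5.2) and does not depend on the column.
- **That the bias is 4.5 percentage points.** One participant in 22 is 4.5%, but that is the granularity of any Arm 4 percentage and does not estimate how many events are moved.
- **That Arm 3's placebo period is seriously corrupted.** Arm 3 events on Days 82–84 do move into its placebo weeks. With a half-life of about three weeks (protocol 4.3), however, Arm 3 remains exposed well beyond Day 84 under any cut.

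**Conclusion.** The point holds and is minor. On the planned schedule, 3 of Arm 4's 84 placebo days (3.6%) are tabulated in its active period; across in-window Week 13 dosing the range is 0 to 6 days. The shift runs one way, from placebo to active, in displays whose stated purpose is that comparison. Separately, three planned on-treatment days are shown with follow-up.

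This assumes dosing within ±3 days and counts the dose date itself as active. The number of events affected cannot be derived from the documents. The overall adverse-event tables and the primary efficacy analysis are untouched, and protocol 4.2.2 says the placebo-first comparisons are not powered. That the cuts were carried over from the Early Termination windows is an inference from matching numbers; the SAP gives no source for them.

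**What to change.** In SAP 6.2.2.2, replace the fixed cuts with participant-level ones:
- **Weeks 13–24** start on the actual Week 13 dose date, or on Day 85 if no Week 13 dose was given.
- **Weeks 25–48** start seven days after the actual Week 24 dose, or on Day 169 if no Week 24 dose was given.
- State that an event starting on the boundary date belongs to the later period. SAP 4.5.2 already treats onset on the treatment start date in this way.

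The second cut should not be Off Treatment Day 1 as such. That date follows the last dose received, so someone withdrawn from treatment on Day 50 would move into Weeks 25–48 from Day 57. Anchoring on the Week 24 dose, with the Day 169 fallback, keeps early discontinuers in the correct study-week band.

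The cost is one derived date per boundary per participant in place of two constants; the dose dates are already collected. One limit remains: an Arm 4 participant who misses the Week 13 dose and starts active drug later still has some pre-active days in Weeks 13–24. A display by study week cannot avoid that, and a footnote should say so. If the sponsor prefers to keep Days 82 and 166, the SAP should give the reason and footnote the affected tables.

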6.2.3. Study Period

Assessments and events will be classified according to the time of occurrence relative to the study intervention period. Off Treatment Day 1 occurs 7 days after the last study treatment dose received, regardless of whether the participant completes treatment as planned or the participant is withdrawn from study treatment.

Study Intervention Period	Definition
Pre-Treatment	Date ≤ Study Treatment Start Date
On-Treatment	Study Treatment Start Date < Date ≤ Off Treatment Day 1 – 1 day
Post-Treatment	Date ≥ Off Treatment Day 1

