6. STUDY INTERVENTION

Study intervention is defined as any investigational intervention(s), marketed product(s), placebo, or medical device(s) intended to be administered to a study participant according to the study protocol.

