6.5.3. Initiation of Nucleos(t)ide Therapy Post GSK3228836 Treatment

Upon cessation of GSK3228836 treatment, participants, regardless of their baseline NA use or not, may experience virological relapse, DNA replication and an ALT flare. Investigators may, at their own discretion and in accordance with local guidelines, decide to initiate new or alternative NA therapy in these participants. Any treatment should be recorded as a concomitant medication.

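### The SAP's safety periods are not aligned to Arm 3's last GSK3228836 dose, so no display it specifies compares post-drug safety over equal windows across arms

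*SAP*

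**What the plan says.** Arm 3 receives GSK3228836 for 12 weeks, "followed by placebo once/week for 12 weeks" (Protocol 4.1). Arms 1, 2 and 4 receive active drug up to Week 24. Placebo counts as study treatment: Protocol Section 6 includes it in the definition of study intervention, and Section 6.1 tabulates it beside GSK3228836.

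SAP 6.2.3 fixes the boundary between periods: "Off Treatment Day 1 occurs 7 days after the last study treatment dose received, regardless of whether the participant completes treatment as planned". On-treatment time is "Study Treatment Start Date < Date ≤ Off Treatment Day 1 – 1 day". The off-treatment footnote in Protocol 1.3 gives the planned date: "the planned first off-treatment visit occurs on Day 169, 7 days after the Day 162 visit". Neither place has a separate rule for Arm 3.

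SAP 6.2.2.2 adds a second scheme: "selected safety displays will be presented by study Weeks 1-12, Weeks 13-24, and Weeks 25-48". Its cuts are Days 1-81, Days 82-165 and Day 166 onward, the same in every arm. Its stated purpose is to contrast active drug with placebo and loading with no loading.

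Protocol 6.5.3 warns: "Upon cessation of GSK3228836 treatment, participants, regardless of their baseline NA use or not, may experience virological relapse, DNA replication and an ALT flare". ALT increase is an adverse event of special interest (Protocol 8.3.7.1, SAP 4.5.2.1).

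**The concern.** The event in Protocol 6.5.3 is tied to stopping the drug, not to stopping injections. The safety objective is framed by regimen: 12 weeks, 12 weeks plus step-down, and 24 weeks. A reader will therefore want to know what happens after each regimen ends. In Arm 3 the first 12 weeks after the drug are labelled on-treatment and tabulated as Weeks 13-24, beside arms still receiving GSK3228836. The Weeks 25-48 column then compares late post-drug time in Arm 3 with early and late post-drug time in the other arms.

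The SAP accepts the principle elsewhere. For SVR, Section 4.2 and Table 3 move Arm 3's assessments to its own end of drug, and give avoidance of bias as the reason. SAP 4.4.3.1 treats Week 36 or Week 48, by arm, as off-drug Week 24, and SAP 4.6.4 counts relapse time from the planned end of drug. Safety has no equivalent step.

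The 6.2.3 rule also labels equal drug exposure in two ways. An Arm 3 participant who stops all injections after Day 78 is post-treatment from Day 85. One who goes on to complete the placebo injections is on-treatment until Day 168.

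**Working it through.** **Inputs.** Visit days and the 7-day rule (Protocol 1.3, SAP 6.2.3); AE window cuts (SAP 6.2.2.2); last planned active dose at Week 12 in Arm 3 and Week 24 in Arms 1, 2 and 4 (Protocol 4.1); matched Arm 3 visits (SAP 4.2).

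**Reproducing the plan's dates.** Week x falls on Day 1 + 7(x − 1), so Week 12 = Day 78, Week 13 = Day 85 and Week 24 = Day 162. Then 162 + 7 = 169, the stated first off-treatment day. The protocol's early-withdrawal example also reproduces (50 + 7 = 57), as does off-treatment Week 24 (169 + 7 × 23 = 330).

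**Equal 24-week window after the last planned active dose.** Arm 3: Days 78 + 1 to 78 + 168, that is 79-246. Arms 1, 2 and 4: Days 162 + 1 to 162 + 168, that is 163-330. Each has 168 days, and both end at a planned visit.

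| How those 168 days are labelled | Arm 3 | Arms 1, 2, 4 |
|---|---|---|
| On-treatment (to Day 168) | 79-168: 90 days (54%) | 163-168: 6 days (4%) |
| Post-treatment (from Day 169) | 169-246: 78 days (46%) | 169-330: 162 days (96%) |
| AE window Weeks 1-12 (to Day 81) | 79-81: 3 days (2%) | 0 |
| AE window Weeks 13-24 (Days 82-165) | 82-165: 84 days (50%) | 163-165: 3 days (2%) |
| AE window Weeks 25-48 (from Day 166) | 166-246: 81 days (48%) | 166-330: 165 days (98%) |

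The two schemes change at slightly different days (169 and 166), so their shares differ a little.

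**Arm 3's full off-drug follow-up.** From 7 days after the last active dose to the last planned visit is Days 85-330, or 246 days. Of these, Days 85-168 (84 days) are on-treatment: 84/246 = 34%.

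**What the Weeks 25-48 column compares.** It opens at (166 − 162)/7 = 0.6 weeks after the last active dose in Arms 1, 2 and 4 and at (166 − 78)/7 = 12.6 weeks in Arm 3. It runs to (330 − 162)/7 = 24 and (330 − 78)/7 = 36 weeks.

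**Visit frequency.** In the first 84 days after the last active dose, Arm 3 has 12 scheduled visits (Days 85, 92, …, 162). The other arms have 5 (Days 169, 176, 190, 218, 246). The post-drug visits SAP 4.2 lists for Arm 3 remove this difference: Weeks 13, 14, 16, 20 and 24 and off-treatment Weeks 4, 8 and 12 are Days 85, 92, 106, 134, 162, 190, 218 and 246. Those are 7, 14, 28, 56, 84, 112, 140 and 168 days after Day 78. Off-treatment Weeks 1, 2, 4, 8, 12, 16, 20 and 24 lie at the same distances from Day 162.

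**The case against.** The strongest reply is that the SAP specifies no off-treatment harm comparison for these labels to damage. AE summaries cover all treatment-emergent events by default (SAP 4.5.2), AESI characteristics cover the whole post-baseline period (4.5.2.1), and laboratory shift tables pool on- and off-treatment time (4.5.3.1). Study Period is named for disposition, AEs leading to withdrawal and reasons for withdrawal (6.1.1). The calendar split serves the active-versus-placebo contrast, for which Arm 3's Weeks 13-24 is indeed a placebo phase shown by arm. Chemistry changes are summarised at every visit, so Arm 3's ALT after Day 78 can be seen. There is no hypothesis test.

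Most of that stands. A reader might infer that half of Arm 3's post-drug events vanish from the safety analysis. They do not: they remain in the overall tables and in the Weeks 13-24 column. A reader might also assume early onset or brief ALT rises and attach a larger figure to misplaced or missed flares. The documents give no onset or duration distribution, so only the day counts are supported.

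Nor does the point justify redefining on-treatment in SAP 6.2.3. Arm 3's placebo injection-site reactions would become post-treatment while injections continue, and Arm 4's placebo weeks would still be on-treatment. The half-life is about 3 weeks (Protocol 4.3), so roughly 2^(−1/3) = 79% of drug remains 7 days after a dose. Where the drug-risk period ends is a judgement.

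What the reply does not answer is alignment. The overall tables mix on-drug and off-drug events, and give Arm 3 36 post-drug weeks against 24. The calendar columns are offset by 12 weeks after the drug. By-visit chemistry means are not an incidence comparison and do not cover adverse events.

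**Conclusion.** The point holds as a gap in alignment. Both safety period schemes ignore Arm 3's change to placebo, so post-drug safety is not compared over equal windows in any display the SAP specifies. Over the matched 24 weeks, 54% of Arm 3's days are on-treatment against 4% in the other arms, and the Weeks 25-48 display holds 48% against 98%. Over Arm 3's full off-drug follow-up the on-treatment share is 34%.

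These counts assume nominal visit days and completion of planned dosing. They measure time, not events, and imply no direction or size of bias in flare rates. Which safety outputs are split by week, and the Study Period used for disposition, are left to the Output and Programming Specification. That document is not among those available, so the statement covers the SAP only. No primary result changes; this is an inexpensive improvement.

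**What to change.** Leave SAP 6.2.3 and the calendar-week displays as they are. In SAP 4.5 and 6.2.2.2, add one set of displays by arm, anchored on the last GSK3228836 dose and covering 24 weeks: AEs, AESIs (including ALT increase) and ALT laboratory values. The planned windows are Days 79-246 in Arm 3 and Days 163-330 in Arms 1, 2 and 4.

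- For scheduled laboratory data, restrict Arm 3 to the post-drug visits already listed in SAP 4.2 (Weeks 13, 14, 16, 20, 24 and off-treatment Weeks 4, 8, 12).
- Footnote that Arm 3 receives placebo injections during the first 12 weeks of this window, so injection-site reactions are not comparable there.
- For participants who stop early, use the actual last GSK3228836 dose. Arm 4 participants who stop before their first active dose have no anchor and should be counted as excluded.

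The data are already collected. The cost is a short SAP edit, one extra table set and a second time axis for Arm 3.

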4.5.2. Adverse Events

An adverse event (AE) is considered treatment emergent if the AE onset date is on or after treatment start date. If AE start date is completely missing and the end date is on or after the treatment start date, the AE will be assumed to be treatment emergent. All AE summaries will be based on treatment emergent events unless otherwise specified.

Adverse events will be coded using the latest version of MedDRA coding dictionary, to give a preferred term and a system organ class. These preferred terms and system organ classes will be used when summarising the data. The severity of AEs and SAEs will be determined by the investigator according to the DAIDS grading system Version 2.1 [National Institute of Allergy and Infectious Diseases. Division of AIDS, 2017], unless specified otherwise in the protocol.

For AEs by maximum grade summary tables, if a participant reports an AE more than once within an SOC/PT, the AE with the most severe intensity will be included in summaries. Relationship to study treatment, as indicated by the investigator, is classified as "not related" or "related". Adverse events with a missing relationship to study treatment will be regarded as "related" to study treatment.

The following table AE summaries will be presented:

- 1. AEs overview: summarize the number and percentage of participants with any adverse event, AEs related to study treatment, AEs leading to permanent discontinuation of study treatment, withdrawal from the study, any serious adverse events (SAE), SAEs related to study treatment, fatal SAEs and fatal SAEs related to study treatment.
- 2. All AEs by system organ class (SOC) and preferred term (PT)

- 3. All AEs by SOC and PT and maximum grade
- 4. All drug-related AEs by SOC and PT
- 5. All drug-related AEs by SOC and PT and maximum grade
- 6. Serious AEs (SAEs) by SOC and PT
- 7. AEs leading to withdrawal from the study by SOC and PT
- 8. AEs leading to permanent discontinuation of investigational product by SOC and PT
- 9. AEs leading to withdrawal from the study by SOC and PT and maximum grade
- 10. AEs leading to permanent discontinuation of investigational product by SOC and PT and maximum grade
- 11. Fatal AEs by SOC and PT
- 12. AEs by overall frequency
- 13. Serious, Non-serious and Drug-Related AEs by SOC and PT (number of subjects and occurrences). This will be presented for Overall, and for Week 1 12, Week 13 24, and Week 25 Week 48.

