6.1.4. Prior and Concomitant Medications

Concomitant medications will be coded using the GSK Drug dictionary. The summary of concomitant medications will be provided by ingredient, i.e., multi-ingredient medications will be summarized for each individual ingredient rather than a combination of ingredients. The summary will be created using ingredient base names, i.e., ingredients with the same base name but different salt will appear under one base name in the summary. Anatomical Therapeutic Chemical (ATC) classifications will not appear in the summary.

A prior medication is defined as any medications that is ended prior to the date of first dose of study drug.

Medications initiated after the first dose of study drug or initiated prior to the first dose of study drug and continued after the first dose of study drug will be counted as concomitant medications. A medication that cannot be determined as prior or concomitant medication due to partially or completely missing start/stop date will be counted as both prior and concomitant medication.

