6.2.6. Handling of Partial Dates

Element	Reporting Detail
General	 Partial dates will be displayed as captured in participant listing displays. However, where necessary, display macros may impute dates as temporary variables for sorting data in listings only. In addition, partial dates may be imputed for 'slotting' data to study phases or for specific analysis purposes as outlined below. Imputed partial dates will not be used to derive study day, time to onset or duration (e.g., time to onset or duration of adverse events), or elapsed time variables (e.g., time since diagnosis). Duration of Hep B infection (years) will be calculated based on year only
Adverse Events	 Partial dates for AE recorded in the CRF will be imputed using the following conventions: Missing start day If study intervention start date is missing (i.e. participant did not start study intervention), then set start date = 1st of month. Else if study intervention start date is not missing: If month and year of start date = month and year of study intervention start date, then If stop date contains a full date and stop date is earlier than study intervention start date, then set start date = 1st of month. Else set start date = study intervention start date. Else set start date = 1st of month.

Element	Reporting Detail	
Bellient	Missing start day and month	 If study intervention start date is missing (i.e. participant did not start study intervention), then set start date = January 1. Else if study intervention start date is not missing: If year of start date = year of study intervention start date, then If stop date contains a full date and stop date is earlier than study intervention start date, then set start date = January 1. Else set start date = study intervention start date. Else set start date = January 1. Else set start date = January 1.
	Missing end day Missing end day and month	A '28/29/30/31' will be used for the day (dependent on the month and year). No Imputation
	Completely missing start/end date	No imputation
Concomitant Medications/Medical History		for any concomitant medications recorded in the CRF ed using the following convention:
	Missing start day	If study intervention start date is missing (i.e. participant did not start study intervention), then set start date = 1st of month.
		Else if study intervention start date is not missing:
		 If month and year of start date = month and year of study intervention start date, then

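### SAP 6.2.3 labels events on the first-dose day Pre-Treatment, contradicting the treatment-emergent rule in 4.5.2, the week windows in 6.2.2.2 and the purpose of the date imputation in 6.2.6

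*SAP*

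**What the plan says.** SAP 6.2.3 (Study Period) gives a single rule for everything that is dated: "Assessments and events will be classified according to the time of occurrence relative to the study intervention period". Its Pre-Treatment row reads "Date ≤ Study Treatment Start Date" and its On-Treatment row reads "Study Treatment Start Date < Date ≤ Off Treatment Day 1", less one day. The first-dose date is therefore the last pre-treatment day. The section has no exception for events and no rule based on clock time.

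Four other SAP sections deal with the same day:

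- 4.5.2: "An adverse event (AE) is considered treatment emergent if the AE onset date is on or after treatment start date". Adverse event summaries rest on this flag unless stated otherwise.
- 6.2.2.2: adverse events have no visit, so "the study week they are assigned to will be based on the AE start date". The Weeks 1–12 window opens at Day 1.
- 6.2.6: if the start day is missing and the month and year match those of first dose, the date becomes the 1st of the month when a complete stop date precedes treatment. In the remaining case the rule is "Else set start date = study intervention start date". The section allows imputed dates to be used for placing data in study phases.
- 6.1.4: a prior medication is one that ended before the first-dose date. Concomitant medications are "Medications initiated after the first dose of study drug or initiated prior to the first dose of study drug" and continued beyond it. A start on the first-dose date is not named.

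**The concern.** An adverse event that begins on the day of the first injection gets two incompatible labels. It is treatment-emergent and in Weeks 1–12 under two sections, yet Pre-Treatment under a third. A programmer following 6.2.3 literally would leave it out of any on-treatment column, and that output would not reconcile with the treatment-emergent tables.

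The imputation rule suffers too. Its branch exists to separate events known to have ended before treatment from those that may have occurred on treatment. Under 6.2.3 both branches give Pre-Treatment, so for study period the branch does nothing.

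**Working it through.** No power or sample-size calculation applies. The check is day arithmetic plus a side-by-side reading.

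**Inputs.** Study day = date − first-dose date + 1 (SAP 6.2.4), so first dose is Day 1. Week x falls on Day 1 + 7(x − 1). Off Treatment Day 1 is 7 days after the last dose (SAP 6.2.3; protocol Table 4 footnote). Placebo counts as study intervention (protocol Section 6).

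**The plan's own figure.** Last planned dose, Week 24: 1 + 7 × 23 = Day 162. Off Treatment Day 1: 162 + 7 = Day 169, the day given in the protocol footnote. It is reproduced.

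**Classification of onset days as written:**

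| Onset | 6.2.3 period | Treatment-emergent (4.5.2) | Window (6.2.2.2) |
|---|---|---|---|
| Day −1 | Pre | no | none |
| Day 1 (first dose) | **Pre** | **yes** | **Weeks 1–12** |
| Day 2 | On | yes | Weeks 1–12 |
| Day 4 (loading dose) | On | yes | Weeks 1–12 |
| Day 85 (Week 13: 1 + 7 × 12) | On | yes | Weeks 13–24 |

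Of these days, only Day 1 conflicts.

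**Length of the on-treatment period for a completer.** As written, Day 2 to Day 168: 168 − 2 + 1 = 167 days. Starting on the first-dose date, Day 1 to Day 168: 168 − 1 + 1 = 168 days, which matches the dosing duration of up to 168 days in protocol 6.1. SAP 4.5.1 also counts the first injection day as exposure, since it adds 1 to the difference between last and first injection dates (162 − 1 + 1 = 162).

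**Partial dates.** Take an event with the day missing, in the month of first dose, and no stop date before treatment. 6.2.6 dates it to the first-dose date. 4.5.2 then makes it treatment-emergent and 6.2.3 makes it Pre-Treatment. An event with a full stop date before treatment goes to the 1st of that month, also Pre-Treatment. The medication rule in 6.2.6 has the same structure.

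**After the change.** With On-Treatment starting on the first-dose date for events, a Day 1 event is On-Treatment, treatment-emergent and in Weeks 1–12. The three rules agree, and no other row of the table changes.

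**The case against.** The strongest reply is that the contradiction touches little of what the SAP plans to show. Adverse event summaries use the treatment-emergent flag, which includes Day 1. The active-versus-placebo and loading-versus-no-loading displays use the week windows (4.5, 6.2.2.2), which also begin at Day 1. Imputing to the start date works as intended for those tables. The explicit promise to present by Study Period is in 6.1.1 (disposition, adverse events leading to withdrawal, reasons for withdrawal). That section takes its period definition from the Output and Programming Specification, which is not among the documents and may already differ from 6.2.3. All of this stands.

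It is also fair that the present inequality suits assessments: 4.1.2 treats Day 1 assessments as pre-dose when time is not collected or equals that of first dose. The fault is only that events share the line.

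On medications, a drug started on Day 1 cannot be prior unless it ended before that date, so concomitant is the only category left. The nucleos(t)ide starts on Day 1 reported in 4.8 are handled as failures in the main estimand and by the supplementary estimand in 4.2.4.3. No efficacy result turns on 6.2.3 here.

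What the reply does not remove is the contradiction. 6.2.3 names events, and an output programmed from it would misplace them.

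**Conclusion.** The inconsistency is real and visible on the face of the SAP, and its consequences are limited. It concerns one calendar day per participant, plus partial dates imputed to that day. It reaches only outputs or derivations that use the 6.2.3 period. Whether any planned output is affected cannot be confirmed without the Output and Programming Specification. The partial-date part assumes that the 6.2.6 rules are the ones programmed; 4.5.2 refers missing adverse event dates to that same specification.

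A reader might infer a bias between arms. Day 1 is the first active dose in Arms 1–3 (66 × 3 × 2 = 396 planned participants), while Arm 4 (22 × 2 = 44) receives placebo on Day 1 and its first active dose on nominal Day 85, inside On-Treatment. First-dose reactions might then seem to be dropped from the loading-dose arms and kept for the arm without loading. The period labels do differ in that way, but the SAP describes no injection site reaction table built on them. The by-week displays count a Day 1 reaction in Weeks 1–12 and a Day 85 reaction in Weeks 13–24. A share of reactions lost per arm would need an assumed risk per dose that the documents do not support, and would describe no planned table.

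**What to change.** 1. In SAP 6.2.3, add a rule for adverse events and medications: Pre-Treatment if Date < Study Treatment Start Date; On-Treatment if Study Treatment Start Date ≤ Date ≤ Off Treatment Day 1 − 1 day. Leave Post-Treatment as it is.
2. Keep the present ≤ rule for Day 1 assessments treated as pre-dose under 4.1.2, and say that it covers assessments only.
3. Bring the Study Period definition in the Output and Programming Specification into line, and check the 6.1.1 display of adverse events leading to withdrawal against it.
4. In 6.1.4, define concomitant medications to include those started on or after the first-dose date.

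The cost is two inequality signs for events, one wording change and a specification check. No data collection changes, and the treatment-emergent and by-week adverse event tables stay as planned.
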